9.2 Sample Size Determination

This is a convenience sample of 20 models to be evaluated by 9 of our Expert Advisory Panel members.

9.3 Populations for Analyses

Expert Advisory Panel.

20 November, 2025

9.4 Statistical Analyses

9.4.1 General Approach

See above. These are established methods of evaluating UX/UI and software usability.

9.4.2 Analysis of the Primary Endpoint(s)

See above.

9.4.3 Analysis of the Secondary Endpoint(s)

See above.

9.4.4 Safety Analyses

N/A

9.4.5 Baseline Descriptive Statistics

Descriptive statistics of the Expert Advisory Panel will include age, sex, primary geography, years of practice in the health economics field, modeling expertise characteristics, and specific expertise in the oncology area.

9.4.6 Planned Interim Analyses

N/A

9.4.7 Sub-Group Analyses

N/A

9.4.8 Tabulation of Individual Participant Data

N/A (Data will be aggregated).

9.4.9 Exploratory Analyses

N/A

10 Supporting Documentation and Operational Considerations

10.1 Regulatory, Ethical, and Study Oversight Considerations

10.1.1 Informed Consent Process

N/A

20 November, 2025

10.1.1.1 Consent/assent and Other Informational Documents Provided to participants

N/A

10.1.1.2 Consent Procedures and Documentation

N/A

10.1.2 Study Discontinuation and Closure

When all study aims/milestones have been achieved.

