1.1 Synopsis

Title:	HModEx®, a cloud-based, centralized health economic model marketplace to reduce costs and enhance equity in cancer
Grant Number:	1R43CA297808-01
Study Description:	The investigators intend to create and test an interactive prototype of an online health economic model platform, HModEx®™, to house oncology models.
Objectives:	
Primary Objective: Create the HModEx® health economic model platform
 
Secondary Objectives: Conduct usability testing of search, quality and collaboration on the HModEx® prototype for 20 oncology health economic models

Endpoints:	
Primary Endpoint: Iteratively unit test 4 tasks (A) Revise model platform and back end, (B) Refine the model taxonomy/characterization (i.e., ontology) and search module, (C) Revamp submission module, and (D) Implement paid modules) individually to ascertain 100% pass of common functionality (e.g., searching, uploading, and evaluating models) in the system back end and then iteratively perform integration testing via the front-end user interface until 100% pass using the System Usability Scale (SUS), a validated questionnaire.
 
Secondary Endpoints: Measure the success of Aim 2 by (1) completion of 80% of tasks in usability testing with scores of ≥ 68 on the SUS, and (2) satisfaction with the site. Testing will focus on user interaction with the system, emphasizing effectiveness, efficiency, engagingness, error tolerance, and ease of learning. Specifically, the investigators will assess the ability of the project team and Advisory Panel members to log into the platform, configure and manage their modeling projects, and annotate or categorize

20 November, 2025

them in accordance with an ontological index. We will assign panelists to interact with at least 2 randomly selected models and associated data files, iterating on this milestone until the investigators achieve 100% success.

Study Population:

Phase* or Stage: National Institutes of Health (NIH) Small Business Innovation Research Phase I Study

Description of Sites/Facilities Enrolling Participants: 9 Expert Advisory Panel Members (4 from US, 5 from UK/Netherlands)

[figure not shown]
Description of Study Intervention/Experimental Manipulation: Development and test of HModEx® prototype health economic model platform with 9 Expert Advisory Panel members

Study Duration*: 1 year

Participant Duration: 8 months

[figure not shown]
20 November, 2025

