on their expertise/interests for further validation. The models will be accessed and evaluated for quality using the CADTH validation assessment tool by our 9 modeler AP members. This validation process will include annotation using the ontology module (Aim 1) and activation of a paid module for premium content; for this first phase, the premium content will be simulated and the paid module will be manually administered. The success of Aim 2 will be assessed via the ability to retrieve a model with the requested search characteristics 90% of the time (Aim 2A, 2B) and complete 80% of tasks in usability testing with scores of ≥ 68 on the System Usability Scale, a validated questionnaire⁸³, and satisfaction with the site (Aim 2C). Testing will focus on how users interact with the system, emphasizing effectiveness, efficiency, engagingness, error tolerance, and ease of learning^{83, 84}; remote usability testing will be conducted using screen-sharing technology. Specifically, the investigators will assess the ability for the project team and AP members to log in, configure/manage their modeling projects, annotate or categorize them according to an ontological index and for each AP member to modify/evaluate at least 2 of the 20 oncology models and associated data files (Figure 4). Panel members will be randomly assigned to thus interact with multiple models; the investigators will iterate on this milestone until 100% achieved. A brief report will be produced that will review quantitative results, qualitative findings, and design recommendations for addressing problem areas. This report will be shared with our AP and will inform any necessary product modifications. The Advisory Panel will be charged with the following responsibilities during alpha and beta testing of our proposed platform:

- 6 members alpha testing for 1 hour each@\$200/hr, which includes uploading an oncology model of your choosing
- 5 members beta testing for 2 hours each for 2 models, which includes interacting with 5 models on the platform

The total remuneration for each Advisory Panel member is up to \$2,000 (\$200/hr*2 hrs*5 models) over the course of 6-12 months after formal awarding of the project.

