4.4 End-of-Study Definition

Achievement of milestones, as above.

20 November, 2025

5 Study Population

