7.1 Discontinuation of Study Intervention/Experimental Manipulation

Upon achievement of all endpoints for both study aims.

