9.1 Statistical Hypotheses

- Primary Efficacy Endpoint(s):

To evaluate the primary endpoints, the investigators will iteratively unit test all 4 tasks individually to ascertain 100% pass of common functionality (e.g., searching, uploading, and evaluating models) in the system back end and then iteratively perform integration testing via the front-end user interface until 100% pass using the System Usability Scale (SUS), a validated questionnaire.

- Secondary Efficacy Endpoint(s):

We will measure the success of the secondary endpoint by (1) completion of 80% of tasks in usability testing with scores of ≥ 68 on the SUS, and (2) satisfaction with the site. Testing will focus on user interaction with the system, emphasizing effectiveness, efficiency, engagingness, error tolerance, and ease of learning. Specifically, the investigators will assess the ability of the project team and Advisory Panel members to log into the platform, configure and manage their modeling projects, and annotate or categorize them in accordance with an ontological index. We will assign panelists to interact with at least 2 randomly selected models and associated data files, iterating on this milestone until the investigators achieve at least 75% success.

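### The panelist model-interaction milestone has two contradictory thresholds (at least 75% and 100%), and the closure rules define no result or end of study if it is missed

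*Protocol*

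**What the plan says.** The milestone concerns panelists working with at least two randomly selected oncology models and their data files. Section 4.1 states its content as the ability "for each AP member to modify/evaluate at least 2 of the 20 oncology models and associated data files". Its threshold appears four times in current text:

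- Protocol 1.1 (Synopsis, secondary endpoints): "iterating on this milestone until the investigators achieve 100% success".
- Protocol 3 (objectives table, secondary row): at least 75%, in the same terms as 9.1.
- Protocol 4.1 (Overall Design, Aim 2): "the investigators will iterate on this milestone until 100% achieved".
- Protocol 9.1 (secondary efficacy endpoint): "iterating on this milestone until the investigators achieve at least 75% success".

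Three sections say when the study ends:

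- 4.4, end of study: "Achievement of milestones, as above".
- 7.1, discontinuation of the intervention: "Upon achievement of all endpoints for both study aims".
- 10.1.2, discontinuation and closure: "When all study aims/milestones have been achieved".

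The synopsis gives a study duration of 1 year. Section 4.1 gives a 6 to 12 month window for the panel's paid work and plans a brief report of the findings. None of these is linked to closure or to a finding that a milestone was missed.

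**The concern.** A criterion with two cut-offs is not fixed in advance: a result between them can be called a success or a failure depending on which section is cited, and that choice could be made after the data are seen. An unseen SAP cannot remove the problem, because the protocol itself states both values.

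The second difficulty is the ending. The milestone is repeated until reached, and every end-of-study provision is worded as success. If the year runs out with the milestone unmet, the written rules neither close the study nor say how the result is reported. Section 10.1.4 says the data will inform a Phase II submission, whose readers need to know which rule applied and whether it was met.

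**Working it through.** The protocol derives no sample size, power or error rate for this milestone, so there is no stated figure to reproduce. The check is a comparison of the passages, followed by an illustration of how far apart the two thresholds lie.

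**Step 1: the passages side by side**

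| Section | Threshold | Repeated until reached? |
|---|---|---|
| 1.1 | 100% | yes |
| 3 | at least 75% | yes |
| 4.1 | 100% | yes |
| 9.1 | at least 75% | yes |

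Sections 4.4, 7.1 and 10.1.2 each name one route to the end, which is achievement. None names a cap on rounds, a date or a not-met outcome.

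**Step 2: what the thresholds mean in counts**

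Input: n = 9 panelists (1.1, 9.2, and the modelers of 4.1). Assumption: one yes/no outcome per panelist.

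- 75% rule: 0.75 × 9 = 6.75, so at least 7 of 9.
- 100% rule: 9 of 9.
- 7/9 = 78% and 8/9 = 89% meet the first rule and miss the second.

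**Step 3: chance of meeting each rule in one round**

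Further assumptions, not in the protocol: outcomes are independent, with a true success rate p of 0.80 or 0.90.

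Formula: P(X ≥ r) = Σ C(n,k) p^k (1−p)^(n−k), summed over k = r to n.

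- p = 0.80: P(7) = 36 × 0.2097 × 0.04 = 0.302; P(8) = 9 × 0.1678 × 0.2 = 0.302; P(9) = 0.8^9 = 0.134. The 75% rule is met with probability 0.738, the 100% rule with 0.134.
- p = 0.90: P(7) = 36 × 0.4783 × 0.01 = 0.172; P(8) = 9 × 0.4305 × 0.1 = 0.387; P(9) = 0.9^9 = 0.387. The 75% rule is met with probability 0.947 (unrounded terms), the 100% rule with 0.387.

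The rules disagree on the same data with probability 0.738 − 0.134 = 0.604 at p = 0.80, and 0.947 − 0.387 = 0.560 at p = 0.90.

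**Step 4: sensitivity to the denominator**

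Section 3 has 8 of 10 panel members doing the evaluation, 5.1 has a panel of 10, and 4.1 has 5 beta testers. The unit could also be the panelist-model pair (9 × 2 = 18).

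| n | 75% needs | 75% rule, p = 0.80 / 0.90 | 100% rule, p = 0.80 / 0.90 |
|---|---|---|---|
| 5 | 4 | 0.737 / 0.919 | 0.328 / 0.590 |
| 8 | 6 | 0.797 / 0.962 | 0.168 / 0.430 |
| 9 | 7 | 0.738 / 0.947 | 0.134 / 0.387 |
| 10 | 8 | 0.678 / 0.930 | 0.107 / 0.349 |
| 18 pairs | 14 | 0.716 / 0.972 | 0.018 / 0.150 |

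The gap is wide in every row.

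**The case against.** **The milestone is not what decides Aim 2.** Sections 1.1, 3 and 9.1 number the success criteria: 80% task completion with a System Usability Scale score of at least 68, and satisfaction with the site. Section 4.1 adds 90% retrieval. The interaction milestone follows these as a description of what panelists will do. This stands. A reader might infer that the conflict can reverse the result of Aim 2, or that Phase II readers would have no result that could be negative. The documents do not support that: the other criteria carry no wording about repeating until passed and can be failed. The conflict reverses only the verdict on this milestone.

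**Repeating until passed does not guarantee a pass.** A reader might infer that the milestone will be met whatever the quality of the prototype. That needs unlimited rounds. The protocol gives a 1-year study, 8 months per participant and pay of up to $2,000 per member, and 6.2 describes two prototype rounds, with 6 and then 9 members. Suppose there were two independent 9-person rounds at a constant p of 0.50, 0.60 or 0.70. One round meets the 75% rule with probability 0.090, 0.232 or 0.463, and two rounds, by 1 − (1 − P)², with 0.17, 0.41 or 0.71. Under the 100% rule the two-round figures are 0.004, 0.02 and 0.08. A miss is therefore quite possible in practice. What remains is that the text does not say what a miss is called or how the study then ends.

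**The success rate is meant to rise between rounds.** A reader might infer that the rate at stopping is inflated merely by selecting the passing round. Section 6.2 has the prototype revised from what each round teaches, so a calculation with a fixed rate does not describe the design, and no such inflation is claimed here.

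**Iteration is normal in development.** Agreed, and it is not criticised. Nor does the protocol make a first-attempt score the only acceptable endpoint: it would score a version since superseded, and it is unclear which session would count as first.

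**The unit of success may be left to a SAP.** Also fair, so its absence is not counted against the plan. The two thresholds and the closure rules are protocol text and cannot be set aside in this way.

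**Conclusion.** The point holds for two defects of wording. First, one milestone under the secondary efficacy endpoint has two incompatible thresholds. With 9 panelists, 7 or 8 successes pass one and fail the other. At assumed independent success rates of 80% and 90%, one round gives 74% against 13%, and 95% against 39%. The contradiction itself needs no assumption; only these probabilities do. Second, 4.4, 7.1 and 10.1.2 recognise only achievement, so the written rules provide no not-met result and no end of study if a milestone is missed within the stated year. This also applies to a failure on the Aim 2 criteria that are not repeated, through the same closure wording. The point does not extend to saying that success is assured or that Aim 2 as a whole is undecided. It should be corrected, in proportion to a small study with no known participant risks.

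**What to change.** 1. State one threshold for this milestone, the same in 1.1, 3, 4.1 and 9.1. Which value is the sponsor's decision.
2. Prespecify which testing round is scored for the milestone. This too is the sponsor's choice; a designated final round would serve. Report the other rounds as development in the brief report already planned in 4.1.
3. Reword 4.4, 7.1 and 10.1.2 so that the study ends when the milestones are achieved or at 1 year, whichever is first, and unmet milestones are reported as not met.

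The cost is a wording amendment plus the decision on which round counts; no extra testing is needed. The downside for the sponsor is that the milestone can then be reported as missed.

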10.1.3 Confidentiality and Privacy

Participant data will be collected using initials only and all data will be kept in a secure Box file with access only on a need-to-know basis.

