2.3 Risk/Benefit Assessment

2.3.1 Known Potential Risks

There are no known potential risks to the proposed research.

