5.1 Inclusion Criteria

10 Expert Advisory Panel members

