5.5 Strategies for Recruitment and Retention

The Advisory Panel members have already been recruited from the PI's knowledge base and the ISPOR Open Source Model Special Interest Group.

20 November, 2025

6 Study Intervention(s) or Experimental Manipulation(s)

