8.4 Unanticipated Problems

8.4.1 Definition of Unanticipated Problems

8.4.2 Unanticipated Problems Reporting

A Data Safety and Monitoring Plan (DSMP) will be developed that will include a brief description of the study design, potential risks and benefits for participating in the study, procedures for data review and reportable

20 November, 2025

events, roles and responsibilities of study staff and the monitoring entity (PI and PhD student), and data management, quality control and quality assurance.

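### Initials as the only identifier let the team see which panelist gave each SUS and satisfaction score, leaving two Aim 2 success measures open to courtesy bias

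*Protocol*

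**What the plan says.** Protocol 10.1.3 sets the identifier: "Participant data will be collected using initials only". The sentence goes on to say that "all data will be kept in a secure Box file with access only on a need-to-know basis". Section 9.4.8 declines individual tabulation because data will be aggregated, and 8.4.2 promises a monitoring plan that will cover data management among other things.

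The participants are a small fixed group. The synopsis (1.1) gives "9 Expert Advisory Panel Members (4 from US, 5 from UK/Netherlands"); 5.1 gives "10 Expert Advisory Panel members". Section 5.5 says they are already recruited, from the principal investigator's own contacts and one ISPOR special interest group. Section 4.1 pays $200 per hour, up to $2,000 per member.

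On the ratings, 6.2.1 has the UX expert build the wireframes, evolve the prototype with the programmer, and run the evaluation sessions. Each participant fills in the SUS when the session finishes. Section 10.1.9.1 assigns collection and analysis to individual team members. Section 6.3, on minimizing bias, deals only with which model goes to which panelist.

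**The concern.** Initials protect identity only where the reader of the data does not know the people. Here the readers know them. A panelist who is paid by the project, may be a professional contact of the principal investigator, and has just spent a session with the prototype's designer has some reason to score generously if the score carries his or her initials.

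The SUS threshold and site satisfaction are both part of how Aim 2 is judged (1.1, 3, 4.1 and 9.1), and 10.1.4 says the data will inform a Phase II submission. A generous tilt would move both measures toward success, and nothing in the protocol would reveal or limit it. Panelists would also have less privacy for their opinions than a coded form would give them.

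**Working it through.** The protocol gives no figure on this point to reproduce. The check has three parts.

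**1. Do initials identify the rater to the team?**
Input from the protocol: panel size n = 9 (1.1, 9.2) or 10 (4.1, 5.1). Assumption, not from the protocol: initials are drawn from M equally likely pairs, with M from 150 (some letters common) to 676 (26 × 26).

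- A given member shares initials with no one else: (1 − 1/M)^(n − 1).
  - M = 150, n = 10: (149/150)^9 = 0.942
  - M = 676, n = 9: (675/676)^8 = 0.988
- All members have different initials: the product of (1 − i/M) for i = 0 to n − 1.
  - M = 150, n = 10: 0.736
  - M = 676, n = 9: 0.948

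A given rater is thus singled out with probability 0.94 to 0.99. The whole panel is free of shared initials with probability 0.74 to 0.95. The accurate statement is nearly every rater, and only to people who have access and know the panel.

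**2. Do the other safeguards separate person from score within the team?**

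| Provision | What it limits | Hides the rater from collectors and analysts? |
|---|---|---|
| Restricted storage (10.1.3) | Access by those without a need to know | No; they need the data |
| Aggregation (9.4.8) | What is tabulated | No; it applies after collection |
| Model assignment rule (6.3) | Prior contact with a model | No; it does not concern ratings |
| Monitoring plan (8.4.2) | Not yet written | Unknown; 10.1.3 already fixes the identifier |

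The protocol describes neither a study code nor private completion.

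**3. Which success criteria are exposed?**

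| Aim 2 criterion | Where | Self-rating? |
|---|---|---|
| SUS of at least 68 | 1.1, 3, 4.1, 9.1 | Yes |
| Satisfaction with the site | 1.1, 3, 4.1, 9.1 | Yes |
| 80% of tasks completed | 1.1, 3, 4.1, 9.1 | No, performance |
| Requested model retrieved 90% of the time | 4.1 | No, performance |

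Two of the four criteria are opinions that a named rater could soften.

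**The case against.** The strongest reply is that the protocol does protect the data, through restricted storage, aggregated reporting and a promised monitoring plan. That is correct. A reader who stops at the word initials might infer that panelists' opinions are unprotected, or that every rating is identifiable to anyone. The rest of 10.1.3, together with 9.4.8, does not support either reading. What remains is identifiability within the team.

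A second reply is that codes change neither payment nor recruitment source, that nothing in 4.1 ties payment to scores, and that the session leader knows who attended. This stands in part. Codes cannot remove a motive to be kind, and observed task performance cannot be anonymous. They can remove the link between a person and a questionnaire score, provided the form is completed out of the session leader's sight.

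A third reply is that inflated opinions alone would not carry Aim 2, because the task and retrieval criteria must also be met. This stands too, and it limits the consequence.

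Two further inferences are tempting. Section 2.3.1 says "There are no known potential risks to the proposed research", while 8.4.2 has the monitoring plan describe "potential risks and benefits for participating in the study". A reader might call this a contradiction, but 8.4.2 lists topics for a plan still to be written, and that plan could record that no risks are known. Section 9.4.5 lists panel characteristics such as age, sex and geography, and a reader might fear that small cells would expose individuals. The protocol proposes no cross-tabulation.

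**Conclusion.** The point holds in limited form. Storage and reporting are restricted, but the identifier in 10.1.3 does not conceal the rater from the people who collect and analyse the scores. SUS and site satisfaction are therefore open to courtesy bias; task completion and retrieval are not exposed in this way.

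The size of the bias is unknown. The protocol gives no expected SUS mean or spread, and does not say whether the threshold applies to the panel mean or to each rater, so any numerical shift would be invented. That the bias would run upward is an inference from payment, recruitment source, identifiability and the timing of the SUS; the protocol neither states it nor rules it out. The identifiability figure rests on the assumed pool of initials and on the team knowing the panel, which 5.5 makes likely.

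This is a worthwhile, inexpensive improvement to a stated rule. It does not undermine the study as a whole.

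**What to change.** - **10.1.3:** replace initials with randomly assigned study codes for the SUS and satisfaction questionnaires. Keep any code list apart from the ratings, with someone who does not analyse them. Do not attach the 9.4.5 characteristics to the coded scores; 9.4.7 plans no subgroup analyses, so nothing is lost.
- **6.2.1:** have panelists complete both forms themselves in a coded web form after the session, unseen by the session leader. Release the scores together once all forms are in, since arrival times could otherwise reveal the rater.
- **2.3.1 (optional):** name loss of confidentiality as a minimal risk.

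The cost is a few sentences and a web form. The team gives up following a low score back to a named panelist, which matters somewhat in iterative design; a free-text comment box on the form would recover part of that. If the 80% task and SUS criteria are meant to be met jointly by each panelist, the holder of the code list would have to make that link. Task performance will still be observed by name, so the protection covers the questionnaires only.
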